#### ***Adverse Event Reporting***

All unanticipated problems (UAPs) involving risks to the participants will be reported to the IRB promptly, but no later than two weeks or 10 business days from the time of identification. An UAP is defined as the following:

- Unexpected (in terms of nature, severity, or frequency) given the information provided in research-related documents and the characteristics of the subject population being studied
- Related or possibly related to participation in the research
- Suggests that the research places subjects or others at a greater risk of harm than was previously known or recognized

Any AE or SAE that is expected, as identified in the study documentation, but is occurring at greater frequency or severity, as determined by the principal investigator's assessment, will be reported to the IRB as a UAP. However, adverse events determined to be unrelated to the study will not be submitted to the IRB.

The study period during which AEs must be reported is normally defined as the period from the initiation of any study procedures to the end of the study treatment follow-up. The start of study procedures is the point of consent. Any AEs which fit the protocol defined reportable events must be reported from the time of consent until study completion.

Information on protocol defined AEs should be recorded immediately in the source document and in the appropriate AE module of the eCRF. All clearly related signs, symptoms and abnormal diagnostic procedure results should be recorded in the source document and grouped under one diagnosis, as appropriate. The clinical course of each event should be followed until resolution or until it is determined at the end of the study that the AE will not resolve.

All injection site events occurring at any time as well as all serious adverse events (SAEs) occurring within 90 days post injection will be collected and compared to published data. It is expected that the AE rates reported for the study will be comparable to those reported in the literature for other corticosteroid and PRP injections.

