## II. Drugs/Biologics/Devices

The biologic under investigation in this study is platelet-rich plasma (PRP), a concentrated solution of platelets of autologous origin. This product will be produced from approximately 15 milliliters of whole blood by a venous blood draw performed by a clinical medical staff within the patient exam room. This sample will be placed into a centrifuge located in the clinical office to collate the platelets within the sample for proper collection of PRP. The 15 milliliters of whole blood will produce approximately 4-6 milliliters of PRP. The volume of PRP administered will be approximately 4-6 milliliters via intraarticular injection in the affected knee of patients with moderate-to-severe knee OA. This amount of PRP is indicated because standard knee injections (a large joint injection) range from 5-10 milliliters of medical substance. The PRP will be administered during the initial visit.

The current standard of care for treatment of moderate-to-severe knee OA involves serial, intra-articular injection of a corticosteroid, with injections performed, at minimum, three months apart. This modality has been shown to provide short-term relief of knee OA symptoms, possibly by modulating the immune response and associated inflammatory cascade and will be used as the reference therapy in this study. However, a limitation of this treatment is a lack of understanding of its impact upon OA pathophysiology, and specifically cartilage degeneration. PRP has been

selected for this study because it has been shown to provide pain relief and increase functionality when administered as described. Moreover, its beneficial effect may persist longer than that of corticosteroid injection, as well as remove the potential for cartilage degradation associated with intraarticular corticosteroid treatment. A corticosteroid study arm is also implemented to compare standard of care treatment to the PRP treatment population.

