## **VI. Number of Subjects:**

Approximately 70 participants will be enrolled. 35 to each arm if funding allows.

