## **VII. Study Procedures/Methods:**

### Enrollment/Randomization/Treatment Visit:

Eligible patients with primary osteoarthritis in at least one knee will be enrolled on a voluntary basis. Prior to the injection, patient-reported outcomes will be quantified using a visual-analog scale (VAS) to assess pain level, a Knee Injury and Osteoarthritis Outcome Score-Joint Replacement (KOOS-JR), and UCLA Activity score to assess functional activity level as part of standard care. These results will be deidentified and analyzed in the laboratory.

The patient will be randomized into one of two treatment arms. If the patient has a history of receiving bilateral knee injections for osteoarthritis and meets study requirements, randomization will occur for both knees. Randomization will be employed using a computer-generated random assignment sequence and results kept in concealed envelopes. The participant will be blinded to the injection regime received.

Enrolled patients will be randomized to one of two treatment arms:

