### **VIII. Potential Risks:**

We do not expect any significant medical risks associated with the treatments presented in this study. Most of the risk associated with this study is related to piercing the skin by injection with synovial fluid collection and the venous blood draw. These can include the following: pain, bruising, bleeding, infection, and damage to surrounding structures, such as nerves and blood vessels. The risks of PRP injections include local infection and pain at injection site. The risks of corticosteroid injections include pain at injection site, skin discoloration, elevated blood sugar, infection, cartilage deterioration, and allergic reaction.

Synovial fluid collection in this study is part of the injection process and a stand-alone procedure at the 4-week visit. It has the same risk as the risk for injections listed previously. If there is a concern with the risks associated with the study, the participants are recommended to ask their provider for more information regarding the risks of the injection to their specific health condition. At any point, the participant has the right to withdraw from the study without recourse.

To help lower these possible risks, only professionally trained individuals will participate in the collection of the specimens. The participant will also be monitored for 5-10 minutes after injection.

All adverse events reported spontaneously by the participant or in response to questioning or observation by the investigator/research staff will be assessed for subject safety, acted upon as needed per situation and be recorded. If the events meet the criteria for IRB reporting, they will be reported to the IRB within five days.

Any adverse event associated with the intervention or deviation from the standard protocol will be evaluated related to subject safety and reporting requirements as well as any potential breach of confidentiality.

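### The only adverse event comparison the protocol names is with unspecified published rates, although a concurrent randomised corticosteroid arm is available

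*Protocol*

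**What the plan says.** Protocol section XII, under Adverse Event Reporting, defines the events as "All injection site events occurring at any time as well as all serious adverse events (SAEs) occurring within 90 days post injection". The comparison and its expected result are then stated together. The protocol says that these events "will be collected and compared to published data. It is expected that the AE rates reported for the study will be comparable", where the yardstick is published experience with both kinds of injection. No publication, rate or margin is named, and the text does not say whether the study's rates are formed by arm or pooled.

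Elsewhere the protocol describes a concurrent control:

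- Section VII: "Enrolled patients will be randomized to one of two treatment arms", one steroid and one PRP.
- Section VI: "Approximately 70 participants will be enrolled. 35 to each arm if funding allows".
- Section II: "A corticosteroid study arm is also implemented to compare standard of care treatment to the PRP treatment population".
- Section VIII gives the products different risk lists. For PRP: "The risks of PRP injections include local infection and pain at injection site". The corticosteroid list adds skin discoloration, raised blood sugar, cartilage deterioration and allergic reaction.

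**The concern.** The protocol makes a positive choice of comparator for adverse events, and it is the weaker of the two available. A rate from the literature reflects that series' patients, event definitions, follow-up and procedures as well as its product. The randomised arms share these features, so the difference between them is protected from such discrepancies.

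The protocol itself gives reasons why published rates may not match:

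- Section VIII describes the 4-week aspiration as a stand-alone procedure with the same risk as an injection, and section XI says that the 4-week visit is not standard of care. A published injection series need not include a second needle entry.
- Section XII has staff question participants about health events at follow-up visits and counts injection-site events whenever they occur. Published series may have looked less hard or for less time.

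Two errors are possible. An excess over the literature that arises from the aspiration or from closer questioning could be attributed to a product. Or both arms could look unremarkable against a loosely chosen rate while differing from each other. With no criterion for comparability, neither would be easy to detect.

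**Working it through.** The protocol states no adverse event rate and no safety calculation, so there is no figure to reproduce. The only input from the documents is n = 35 per arm (section VI). **All event rates below are assumptions.**

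**1. What one arm can show by itself.** Exact (Clopper-Pearson) 95% intervals:

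- 0/35: upper limit 1 − 0.025^(1/35) = 10.0%, so 0 to 10.0%
- 1/35 (2.9%): 0.07% to 14.9%
- 3/35 (8.6%): 1.8% to 23.1%

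With no events, any published rate up to about 10% lies inside the interval. Without a criterion, all such rates could be called comparable.

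**2. How added procedure risk shifts the rate.** Suppose each needle entry carries risk p, the two entries are independent, and aspiration events are counted. The risk of at least one event is then 1 − (1 − p)². For p = 5% this is 1 − 0.95² = 9.75%. Both arms have the aspiration, so the shift largely cancels between them. It does not cancel against an injection-only series.

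**3. False excess against a fixed published rate.** Find the smallest count r with P(X ≥ r | 35, published rate) ≤ 0.025, then evaluate P(X ≥ r) at a true rate common to both arms.

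| Published rate | r | True rate, both arms | Probability of a false excess |
|---|---|---|---|
| 5% | 6 | 10% | 13% |
| 5% | 6 | 15% | 43% |
| 10% | 8 | 20% | 40% |
| 10% | 8 | 30% | 87% |

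The products do not differ in any row, so a between-arm comparison would not carry this error.

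**4. What the between-arm comparison can show.** Power with 35 per arm, two-sided 0.05, normal approximation (Fisher's exact test in brackets):

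- 5% v 15%: 28% (14%)
- 5% v 20%: 47% (33%)
- 10% v 20%: 21% (13%)
- 10% v 30%: 55% (46%)

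The between-arm contrast removes the mismatch with the literature but is imprecise.

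**The case against.** **Analysis detail belongs in the SAP.** By-arm adverse event tables are commonly left to the SAP, which is not shown, and nothing in the protocol rules them out. That stands: the absence of such a table is not itself the point. The point is that the protocol names a comparator, chooses the external one, and states the expected result. A by-arm table in a SAP would leave that text in place.

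**A literature benchmark has a purpose here.** This also stands. Adverse Event Reporting requires IRB notification when an expected event is judged to occur at greater frequency, and the definition of an anticipated event refers to incidence known from published literature, among other sources. A between-arm difference cannot show that both arms exceed expected rates, for example because of the shared aspiration. Published rates should therefore be kept, in a supporting role.

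**Stronger readings go too far.** A reader might infer that the trial's safety conclusion rests on a biased and uninformative comparison. The documents do not support that:

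- No safety objective, endpoint, hypothesis or decision rule is defined, so there is no formal safety conclusion. The sentence sits in the monitoring plan, and it states an expectation.
- Bias is a risk. With no rates or sources given, neither its direction nor its size can be established.
- The historical comparison is not shown to be uninformative. If the published rate truly applied, it would have more nominal power than the concurrent one (5% v 20%: 73% against 47%; 10% v 30%: 87% against 55%).
- The wide intervals come from 35 per arm and would affect either comparator.

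**Conclusion.** The point holds in limited form. For injection-site events and 90-day serious adverse events the protocol names only an external comparator, without source, rate or criterion, while a randomised comparator with the same population, ascertainment and aspiration is available. A mismatch with the literature could be taken for a product difference or could conceal one.

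Under the assumed rates, a mismatch of 5% against 10% gives a false excess 13% of the time, and 10% against 20% gives 40%. These figures assume a formal exact one-sided 0.025 comparison of one arm of 35, which the protocol does not prescribe; they illustrate how far a mismatch could mislead and do not predict what will happen. The weakness is real and cheap to correct. It does not touch the primary objective or the sample size.

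**What to change.** In section XII, Adverse Event Reporting, replace the two sentences on comparison with published data and expected comparability by wording to this effect:

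> Injection-site events and SAEs within 90 days will be tabulated by randomised arm. The main comparison is descriptive: the PRP minus corticosteroid difference in the proportion of participants with at least one event, with an exact 95% CI. Published rates, with their sources named, will be given as context and used as the reference when judging whether expected events occur at unexpected frequency. No claim of comparable safety will be made.

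Two features of the design must be covered in the same place:

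- **Later injections.** Section XI lets participants choose an injection type at a visit for recurrent pain. Events after a patient-chosen injection should be shown separately, because the randomised contrast no longer applies cleanly to them.
- **Both knees randomised.** Section VII randomises both knees of eligible bilateral participants. For them, count injection-site events by knee, and list SAEs separately when they cannot be attributed to one arm. The exact interval assumes independent participants, so it should not treat two knees of one person as two people.

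The cost is a short protocol amendment and one table from data already being collected. The downside is a wide interval: 0/35 in a single arm already leaves up to 10.0% open, and the difference between two arms will also be imprecise. The result is an estimate and will not serve as a powered safety test.

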### **XIII. Statistics/Power:**

The number of subjects per group was determined from a pre-study power analysis using previously published data on prevalence of OA biomarkers and reported symptomatology

